Appendix 1 - Study Procedure: Application phases, randomised distribution of participants and assessment moments	24
Appendix 2 : Bi-REAL: 12-Session DBt-ST programme for Bipolar Disorder Layout	25
Appendix 3: Timing of Measures Completed by Participants.....	26
Appendix 4: Diary card	27

1. GLOSSARY of Terms and Abbreviations

ABED	Associação de Apoio aos Doentes Depressivos e Bipolares
AR	Adverse Reaction
BD	Bipolar Disorders
BSD	Bipolar Spectrum Disorder
DBT	Dialectical Behaviour Therapy
FPCEUC	Faculty of Psychology and Educational Sciences – University of Coimbra
FMUC	Faculty of Medicine – University of Coimbra
HMDS	Hamilton Depression Scale
ICF	Informed Consent Form
Participant	An individual who takes part in a clinical trial
RCT	Randomised Controlled Trial
REC	Research Ethics Committee
SAE	Serious Adverse Event
ST	Skills Training
UC	University of Coimbra
YMRS	Young Mania Rating Scale

2. SUMMARY/SYNOPSIS

Short Title	BI-REAL: a 12-session DBT Skills Group Intervention adapted for Bipolar Disorder – a feasibility Randomized Pilot Trial
Methodology	Feasibility study with a two-arm randomised parallel controlled trial design
Research Sites	University of Coimbra - Center for Research in Neuropsychology and Cognitive and Behavioral Intervention (CINEICC)
Objectives/Aims	To assess the feasibility and acceptability of a future definitive randomised controlled trial (RCT) evaluating the feasibility and acceptability of a Dialectical Behaviour Therapy Skills intervention for adults with bipolar and related disorders
Number of Participants/Patients	60
Main Inclusion Criteria	
Client group: individuals with a Diagnosis of Bipolar and Related Disorders:
 
Inclusion criteria:
 
 i) aged 18 or over ii) lifetime diagnosis of Bipolar Disorder (I,II, "other specified bipolar disorder") or Cyclothymic Disorder, according to DSM-V iii) mood instability (at least one complete mood episode in the last 5 years, and reported interference of sub-clinical mood symptoms) iv) Sufficient competency in Portuguese to be able to complete study measures without the need for translation. v) Having access to means to participate in the online group (i.e. access to a stable internet connection, having a functional camera and microphone on their computer, and zoom) 
Exclusion criteria:
 
 i) current high risk of suicide (measured through clinical interview) ii) Bipolar disorder secondary to an organic cause; iii) Diagnosis of substance dependence or continuous illicit substance misuse resulting in uncertain primary diagnosis;

	iv) Acute episode of mania, hypomania or major depressive episode (at baseline) or not euthymic. v) Other high-risk pervasive disorders such as Borderline Personality Disorder; persistent self-injury; vi) the person lacks capacity to consent to treatment, low insight vii) Receiving psychological specific treatment for BD
Statistical Methodology and Analysis (if applicable)	Quantitative analysis: descriptive, linear mixed models Qualitative analysis: qualitative interview and questionnaire assessing programmes utility, acceptability and satisfaction
Proposed Start Date	01.02.2020
Proposed End Date	31.08.2022
Study Duration	24 months from obtaining approvals to delivery of intervention programme to the experimental group, and assessment of all participants 6 month after randomisation; plus 6 months post data collection for production of a report.

3. SCIENTIFIC RATIONALE

Bipolar disorder (BD) is a serious mental disorder characterised by episodes of mania, hypomania, and depression, occurring with a typically cyclical course (Johnson, 2004). In addition to mood instability, BD has been associated with significant functional impairment, lower quality of life, and higher rates of suicide compared to the general population (Pompili et al., 2014). Despite advancements in pharmacological and non-pharmacological treatments, BD often involves recurring episodes and subclinical symptoms within episodes (Geddes & Miklowitz, 2013). Predicting the course and outcome of the disorder remains challenging. BD ranks as the sixth leading cause of disability-adjusted life years worldwide, imposing substantial costs on society, patients, and mental health services (Vos et al., 2020).

Even though the aetiology of BD is still unclear, it is considered multifactorial, involving a combination of genetic and environmental factors. While fewer studies have explored the role of psychosocial factors in the development and maintenance of BD, some risk factors have been identified. Negative

early experiences, family characteristics, and adverse life circumstances have been implicated. Research has also found higher levels of childhood abuse and current internalised shame in individuals with BD compared to control groups. Stressful life events may act as triggers for affective symptoms, and individuals with BD often face stigma, which can negatively impact their social and occupational functioning (Fowke et al., 2012). Pharmacological interventions prevail as the primary management tool in BD. However, most patients are not fully stabilised on drug therapies alone, and a large number of patients experience residual symptoms; thus, full functional recovery is uncommon (Geddes & Miklowitz, 2013; Roth & Fonagy, 2005). Hence, growing evidence and international guidelines support the need to use psychosocial interventions as adjuvant therapies to improve recovery in BD (C. Henry et al., 2011; Slade & Longden, 2015).

Our research adopts a recovery-based perspective, aiming to foster hope, understanding, and empowerment while striving for a meaningful and satisfying life, with less emphasis on clinical outcomes. Recovery in mental health encompasses more than the traditional clinical definition focused on symptom reduction, hospitalisation rates, and medication adherence. It emphasises achieving a better quality of life despite ongoing clinical symptoms (Jones et al., 2013).

Psychoeducation (PE) and Cognitive-Behavioral Therapy (CBT) are the most extensively studied psychosocial interventions for BD, with some evidence supporting their efficacy (Colom et al., 2009; NICE, 2014; Salcedo et al., 2016). However, there are also contradictory findings contesting their efficacy, and that is why there are still no consensual Gold standard psychosocial interventions in BD (Geddes & Miklowitz, 2013). A systematic review regarding empirically supported psychosocial interventions for BD suggested Dialectical Behavior Therapy (DBT) as a promising treatment for BD needs further research (Salcedo et al., 2016). Nonetheless, standard DBT and the available evidence of its efficacy mainly target key psychological and interpersonal processes hypothesised to contribute to negative emotion (e.g. anger, sadness) but does not address or help clients to manage high/hypomanic mood states present in BD, which demands an adaptation of the standard skills training to BD. We took that into consideration and the work of DiRocco et al. (2020), along with the DBT skills workbook that Van Djick (2009) developed for people with BD, and developed a 12-session skills intervention programme. A couple of studies have examined modified versions of DBT as an intervention for Bipolar Disorder for adolescents and adults, with preliminary encouraging results (Goldstein et al., 2014; Van Dijk et al., 2013; Wright et al., 2018). Even so, none has been fully powered randomised controlled trial or included individuals across the BSD, and there is no evidence, as far as we know, that any intervention programme with DBT for BD was conducted in Portugal. Thus, DBT seems to be a promising approach, given its components for emotion regulation, and has shown some

preliminary findings to reduce depressive and manic symptoms as well as to improve emotional dysregulation in BD groups (Goldstein et al., 2007; Van Dijk et al., 2013).

This study aims to investigate if our programme Bi-REAL (Respond Effectively and Live mindfully), a 12-session online DBT skills intervention for BD, is acceptable and feasible and if it shows preliminary improvements in selected variables connected to recovery and emotional regulation and other psychological processes, in a randomised controlled pilot trial.

4. TRIAL AIMS

1. To inform the recruitment and timeline of a future fully powered trial by establishing the number of participants identified, approached, consented, randomised and completed.
3. To refine future trial procedures by establishing the acceptability and experience of the trial process to participants, including randomisation and completion of outcome measures.
4. To determine the optimal primary outcome measure in a future trial by assessing the performance of selected candidate primary outcome measures with respect to the level of acceptability to participants (completion rates) and participant-perceived relevance and value, and based on some additional secondary measures that are thought to improve with DBT-ST.
5. To inform estimation of sample size for a future trial by measuring data completeness at follow-up (participant attrition).
7. To further assess the acceptability of the treatment via qualitative interviews and, based on input from trial participants and clinicians, to further refine and develop the treatment manual and the procedures for training trial therapists.

4.1 General aims

We will also evaluate whether the following criteria have been met prior to planning a future definitive trial:

1. Trial participation does not lead to serious negative consequences (unexpected adverse reactions) for our participants.
2. Any serious concerns about the acceptability and feasibility of the trial procedures can be rectified prior to a full trial.
3. Follow-up data at 3 months is available from at least 60% of participants.
4. At least 60% of patients complete treatment (attend at least 50% of possible sessions).

5. METHOD

5.1 Research Design

Our feasibility study is a two-arm randomised parallel controlled trial design: where we intend to have 60 participants that will be randomised on a 1:1 ratio to Treatment as Usual (TAU) [control arm] or Bi-REAL programme plus TAU (TAU + Bi-REAL) [intervention arm]. Outcome measures will be recorded at baseline and at post-intervention (3 months after baseline) and with a follow-up point at 3 months after treatment ends (6 months post-randomisation). See appendix 1 for more detail.

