If the participant is eligible for the study, they will then complete the baseline self-report measures (see Appendix 3): measures assessed by the clinician will take place during the assessment (i.e. CIBD, YMRS and HMDS), and the self-report measure will be sent via link to be completed online. Participants in the experimental group will additionally fill in an adapted diary card and submit it once a week (between sessions), where they are asked to rate their emotions intensity and use of skills (see Appendix 4). Additionally, after each session participants will be asked to anonymously fill in the Group Session Rating Scale (GSRS; Duncan et al., 2003) which briefly assessed participants experience of the group regarding relationships in the group, goals and topics, approach/method, and overall cohesion. Following randomisation (more details in that section) participants will be followed up by the research team at 3 and 6 months post baseline. At 3 month follow up (post-randomisation) blinding was not

conducted considering the need to conduct a qualitative interview of the intervention programme. Independent clinicians and researchers conducted these interviews, and the qualitative interview was anonymised so that participants could share their experience freely about the facilitators, programme and group. All the assessment moments are described in Appendix 1 and the assessment measures per moment in Appendix 3.

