5.8 Randomisation Procedure

Following completion of the baseline assessment, eligible participants will be randomised on a 1:1 ratio (minimisation by age and psychological support status [undergoing psychotherapy versus not receiving psychological support]) to Treatment as Usual (TAU) [control arm] or Treatment as Usual plus Bi-REAL programme (TAU + BI-REAL) [intervention arm]. We will perform a stratified block randomization after participant has attended a baseline assessment and has consented to the trial, a member of the research team will enter a set of data on the randomisation website (www.randomization.com). Participants will receive an email informing them of the arm to which they have been allocated. For participants allocated to the intervention arm, they will be informed at the group starting date and time.

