5.10 Measures

The following measures where used, to assess diagnosis, clinical symptoms and self report:

Diagnosis and mood episode/functionality/empowerment (completed at baseline and 3, 6 months post baseline):

- Clinical Interview for Bipolar Disorder (CIBD; Azevedo et al., nd) – Clinical semi-structured interview which allows for the diagnosis of Bipolar and Related disorders. It includes an

assessment of mood symptoms interference and empowerment towards bipolar symptomatology by the interviewee – outcomes considered will include empowerment and interference of mood symptoms

- Young Mania Rating Scale - observer rated, measures current mania symptoms
- Hamilton Depression Scale - observer rated, measures current depressive symptoms

5.10.1 Primary outcomes:

- BIPOLAR DISORDER RECOVERY QUESTIONNAIRE (Jones et al., 2013), a 36 item self-report measure that has been developed to measure personal recovery in people with Bipolar Disorder.
- BRIEF QUALITY OF LIFE IN BIPOLAR DISORDER SCALE(Michalak et al., 2010), a self-report measure of quality of life in bipolar disorder that has been specifically designed for and validated with individuals with the condition.

The additional measures selected for this study include secondary outcomes we believe might change due to the skills developed in the programme, and some hypothesised mechanisms of change, providing data on their performance and preliminary analysis of change. Hypothesised treatment targets include difficulties in regulating emotions, hyper/hypo activation, emotional acceptance, emotional awareness, self-reassurance, self-criticism (hated selfxxx) and shame.

5.10.2 Self-report measures of therapy process (completed at baseline, 3, and 6 months post baseline):

- Depression Anxiety and Stress Scale (DASS-21) (Henry & Crawford, 2005) – we will use the depression and anxiety subscales to assess the psychological distress.

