- Forms of Self-Criticising/Attacking & Self-Reassuring Scale (FSCRS) - (Gilbert et al., 2004) is a 22-item self-report questionnaire in which participants are asked to rate how they typically think and react when things go wrong for them. To a first probe statement: “When things go wrong for me...” participants respond on a 5-point Likert scale (ranging from 0 = not at all like me to 4 = extremely like me). A scale has three factors: Inadequate Self (e.g. ‘I think that I deserve my self-criticism’; ‘I remember and dwell on my failings’); Hated Self (e.g. ‘I stop caring about myself’; ‘I do not like being me’); Reassured Self (e.g. ‘I still like being me’; ‘I can feel lovable and acceptable’).

5.10.3 Measures completed session by session by participants in Bi-REAL + TAU condition.

- Online Version of Diary card submitted before each session (see Appendix 4);
- Group Session Rating Scale (GSRS; Duncan et al., 2003) participants are asked to fill in this assessment scale after each session in an anonymous way to decrease social-desirability bias; this measure uses a four-item visual analogue scale designed to assess key dimensions from 0 to 40: Relationship (0 – *“I did not feel heard, understood, respected, and/or accepted by the leader and/ or the group”* to 40 - *“I felt heard understood, respected, and accepted by the leader and the group”*); Goals and Topics (0 – *“We did not work on or talk about what I wanted to work on and talk about”* to 40 - *“We worked on and talked about what I wanted to work on and talk about.”*); Approach or Method (0 – “The leader and/ or the group's approach is not a good fit for me” to 40 – “The Leader and group's approach is a good fit for me.”); and Overall (0 – “There was something missing in group today - I was not engaged” to 40 – “Overall today's group was right for me - I felt engaged”).

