6. STATISTICAL CONSIDERATIONS

6.1 Sample Size

60 participants (30 per group) will allow us to address the stated objectives of this feasibility trial. This represents recruitment to Bi-REAL at full capacity (10 per group), with equivalent numbers randomised to TAU. Previous studies with this population estimate an attrition rate of 17% (with respect to the primary end point at nine months post-randomisation. Our sample size of 48 will allow us to estimate this level of attrition for a future definitive trial with a precision of $\pm 15\%$ with 95% certainty.

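### Do the 3- and 6-month visits still match the end of treatment if a therapy group starts some time after baseline?

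*Combined protocol and SAP*

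**What the plan says.** Section 5.1 (Research Design) places outcome measurement at baseline, then "at post-intervention (3 months after baseline) and with a follow-up point at 3 months after treatment ends (6 months post-randomisation"), and refers to Appendix 1 for detail. Other sections count from trial entry only. The synopsis has "assessment of all participants 6 month after randomisation", Section 5.7 says "participants will be followed up by the research team at 3 and 6 months post baseline", and Section 5.10.2 has the process measures "completed at baseline, 3, and 6 months post baseline". The table in Appendix 3 names the same two visits by their relation to treatment: a post-treatment column, then a three-month follow-up column.

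Treatment begins on a group date. Section 5.8 randomises individuals after baseline and adds: "For participants allocated to the intervention arm, they will be informed at the group starting date and time". Section 6.1 sets the group size: "This represents recruitment to Bi-REAL at full capacity (10 per group), with equivalent numbers randomised to TAU".

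No session frequency is stated outright. Section 5.7 asks intervention participants to "fill in an adapted diary card and submit it once a week (between sessions"), and Section 5.10.3 lists the "Online Version of Diary card submitted before each session". Together these imply weekly meetings.

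Section 4.1 lists four criteria to evaluate before a definitive trial is planned. The third requires follow-up data at 3 months from at least 60% of participants.

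**The concern.** A visit cannot always fall both 3 months after baseline and at the end of treatment when treatment starts on a group date. Filling one group of 10 means randomising about 20 people, so those randomised first could wait.

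If visits follow the calendar, a person who waited would give post-intervention scores and the programme interview before the programme was over. Their last visit would also come less than 3 months after treatment ended. If visits instead follow the end of treatment, TAU participants have no matching date, and the arms could be measured at different times since randomisation. Either way the 3- and 6-month summaries and the exploratory time-by-group models would be harder to read.

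There is also a labelling question. Section 5.7 uses the 3-month follow-up for the visit 3 months after randomisation, while Appendix 3 gives that name to the later visit. The third criterion in Section 4.1 could therefore seem to refer to either of two visits about 3 months apart.

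**Working it through.** **Inputs.** There are 12 sessions plus one pre-session (Section 5.5, Appendix 2). Weekly spacing is inferred from Sections 5.7 and 5.10.3. Visits are at 3 and 6 months (Section 5.1). With a month of 30.44 days, these fall on about day 91 and day 182.6. Let *w* be the days from baseline to the first meeting, with randomisation taken as close to baseline. Let *S* be the days from first meeting to session 12:

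- *S* = 77: pre-session and session 1 in the same week, 11 × 7.
- *S* = 84: pre-session one week before session 1, 12 × 7.
- *S* = 91: as for 84, with one week skipped (here after session 6).

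**The plan's own schedule.** With *w* = 0 and *S* = 91, treatment ends on day 91. The 6-month visit follows 182.6 − 91 = 91.6 days later, and 91.6 / 30.44 = 3.01 months. Section 5.1 is therefore reproduced when the group starts at once.

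**Slack.** The largest wait with treatment finished by day 91 is 91 − *S*, which gives 14, 7 and 0 days.

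**Effect of a longer wait.** Sessions held by day 91 are counted from the spacing above. The gap from treatment end to the last visit is (182.6 − *w* − *S*) / 30.44 months.

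| *S* (days) | Largest wait (days) | Sessions by day 91, *w* = 14 | Sessions by day 91, *w* = 28 | Gap, *w* = 14 (months) | Gap, *w* = 28 (months) |
|---|---|---|---|---|---|
| 77 | 14 | 12 | 10 | 3.01 | 2.55 |
| 84 | 7 | 11 | 9 | 2.78 | 2.32 |
| 91 | 0 | 10 | 8 | 2.55 | 2.09 |

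**How long could a wait be?** The documents do not say. The intervention arm needs 30 / 10 = 3 groups, so 60 / 3 = 20 people are randomised per group. If those 20 baselines are held together just before the group starts, waits are days. For an outer bound, the synopsis allows 24 months including 6 months of follow-up, which leaves 24 − 6 = 18 months to randomise 60. That is 60 / 18 = 3.33 per month, and 20 / 3.33 = 6.0 months to fill one cohort. This assumes an even pace and no batching. It is a limit and not a forecast.

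**Labels.** Section 5.7 ties its 3-month visit to randomisation, and Section 6.2 reports at three and six months. Section 5.1 equates 3 months after treatment with 6 months after randomisation, which identifies the last column of Appendix 3 as the 6-month visit. The natural reading of the third criterion is the visit 3 months after randomisation, with a threshold of 0.60 × 60 = 36 participants. Section 6.2 also promises completion levels at both visits.

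**The case for a change.** The best argument for a change is that the readable text has no maximum wait, no visit window, no rule for batching baselines, and no statement of which clock prevails. With steady enrolment and no batching, even the first person in each group would wait no more than about 2 weeks only if all 60 enrolled in about 1.5 months: 60 / 1.5 = 40 per month, and 19 / 40 = 0.475 months, or about 2.1 weeks. The programme interview depends on treatment having finished, and the 6-month question about retained skills is affected by time since it ended. Stating a single clock would need mainly wording.

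The arithmetic stands. The conclusion drawn from it is weaker, for three reasons.

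- **The gap cannot be established.** Sections 5.1, 5.6 and 5.7 all send the reader to Appendix 1 for procedure or assessment timing. Its title covers recruitment phases, allocation and assessment points. The chart is lost from the available text, so silence elsewhere does not show that the plan lacks a rule.
- **The text does not force the harmful reading.** Section 5.9.1 puts the acceptability questionnaire at the end of the programme, and Appendix 3 calls the visit post-treatment. Section 5.1 plainly intends about 3 months from baseline to the end of treatment, which fits baselines held shortly before each group.
- **The obvious remedy is a trade-off.** Timing both arms from group start would place session 12 (day 77 to 91) no later than the 3-month visit whatever the wait. But time since randomisation would then vary between people, and TAU participants would be timed from a group they do not attend. Some follow-ups would come later, as would the programme offered to TAU after the 6-month visit (Section 7.2). The wait itself would be no shorter, and the baseline scores would be just as old when the group began.

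**Conclusion.** No change is needed. The two descriptions of each visit agree if groups start within about 0 to 2 weeks of baseline, assuming weekly sessions and at most one skipped week. Nothing in the documents shows longer waits. At a 2-week wait, 10 to 12 of 12 sessions are held by the 3-month visit and the post-treatment gap is 2.5 to 3.0 months. At 4 weeks the figures are 8 to 10 sessions and 2.1 to 2.5 months, but that wait is hypothetical.

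Counting from randomisation is a legitimate choice that gives both arms the same clock. Its price is some imprecision in treatment-relative timing. That is acceptable where Section 6.2 makes the initial analysis descriptive and the mixed models exploratory. Recruitment and attendance counts do not depend on visit dates. Analysts who have the group start dates can describe the interval when they report.

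The double use of 3 months is a clerical slip. Section 5.1 shows which visit Appendix 3 means, and completion is to be reported at both visits, so the third criterion can be judged openly. This verdict would need another look if the Appendix 1 chart contradicted Section 5.1 or the trial's records showed waits of 4 weeks or more.
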